6.1.3.2 EXCLUSION OF DATA FROM SAFETY ANALYSIS

Not applicable

6.2 PHASES AND TIME POINTS

6.2.1 Phases

Adverse events, medications, and procedures will be allocated to phases. All other analyses will not be allocated to phases. Instead, the visit and time point labels indicated on the subject's electronic case report form (eCRF) will be used to allocate the assessments. Early termination assessments will be allocated to the treatment phase.

Adverse events and medications:

Phase	Start	End
Screening	Date of signing the ICF, with 00:00 added as time part	First administration date(time) – 1 minute
Treatment	First administration date(time)	Date of last contact, with 23:59 added as time part

Per definition, and for each subject, the first phase starts on the date of the earliest available ICF signature, with 00:00 added as time part. The last available phase ends on the date of last contact, with 23:59 added as time part.

Procedures:

Phase	Start	End
Screening	Date of signing the ICF	First administration date – 1 day
Treatment	First administration date	Date of last contact

Per definition, and for each subject, the first phase starts on the date of the earliest available ICF signature. The last available phase ends on the date of last contact.

AEs, medications, and procedures will be allocated to phases as described in sections 3.1.2 and 5.5.2 respectively.

All PK records (PK concentrations and PK parameters) and IHRs will be allocated to the treatment phase.

	Statistical Analysis Plan	
CLI-10067AA1-01	Final Analysis	Final 1.0 of 30MAY2024

6.2.2 Baseline and change from baseline

The baseline value is the last non-missing value, including unscheduled assessments, before the administration of the study treatment. In case this results in more than one record with the same date and time, the unscheduled record is selected as baseline.

Note: decisions on whether a different baseline should be used in the analysis will be fully documented in the DRR.

Change from baseline is defined as:

Change from baseline at time point t = value at time point t – baseline value.

Relative change from baseline at time point t is defined as follows:

- When baseline value is not zero: $100*((\text{value at time point t} - \text{baseline value}) / \text{baseline value})$
- When both baseline value and value at time point t are zero: not calculated
- When baseline value is zero and value at time point t is not zero: not calculated

6.2.3 Relative day

Relative days (DY) will be calculated according to the following rule:

- Concerned date < reference date: DY = concerned date – reference date
- Concerned date \geq reference date: DY = concerned date – reference date + 1

The reference date is the date of administration of study treatment.

6.2.4 Analysis visits

The analysis will use the visits indicated on the subject's eCRF, while for the time points related to the PK concentration data and the vital signs and oxygen saturation assessments a windowing approach will be used (see time window definitions below). For PK parameter calculation the actual sampling time will be considered, as reported in section 2.1.2.

The screening value is the last available and non-missing value before Day 1. This value corresponds to the screening visit, except in case of retesting. Reason for this approach is the use of retest results for subject eligibility assessment.

Unscheduled assessments will not be used in the analysis unless it is selected as screening value, or per time window definitions below.

The unscheduled assessments will be checked during the data review meeting before database lock, and any different approach to the rule defined above will be documented in the data review report.

Baseline is defined in section 6.2.2.

All scheduled and unscheduled assessments will be listed.

Statistical Analysis Plan

CLI-10067AA1-01

Final Analysis

Final 1.0 of 30MAY2024

Except when defined by time windows, the analysis visit labels will be assigned using the following rules:

- All planned screening, re-screening, eligibility recheck, etc. visits occurred during the screening phase will be presented as 'Screening'.
- All planned visits occurred during a scheduled day, will be presented as 'Day x' (x = study day, e.g. 'Day -1', 'Day 1', etc.)
- Early termination visits will be presented as 'Early Termination'
- Unscheduled visits will be presented as 'Unscheduled' unless the decision to reallocate the visit is fully documented in the DRR. In case of reallocation, the unscheduled visit will be presented with the same label as the replaced planned visit (see rules above)
- Other visits not covered by the rules above will be presented using similar labels to the ones used in SDTM (XX.VISIT)

For PK data, AVISIT(N) will be assigned per PK profile of interest and will be based on the eCRF visit of the corresponding study treatment administration.

The analysis time point labels for pharmacokinetic concentration data, vital signs and oxygen saturation, will be assigned using the following time windowing rules.

Next to the screening value, all assessments, including unscheduled assessments, will be allocated to analysis windows. Tables will present the analysis windows as defined below and listings will present the analysis windows, as well as the eCRF visits. Allocation of assessments will be done according to the following tables:

Pharmacokinetics:

Analysis time point window	Target time after end of infusion (hours)	Time interval (hours)
Pre-dose	<0	Last day 1, pre-dose assessment
EOI	0	[0 min; 10 min=0.1667]
2h	2	[11 min=0.1833; 3]
4h	4	[3.0167; 6]
8h	8	[6.0167; 14]
20h	20	[14.0167; 58]
Day 5	96	[58.0167; 120]
Day 7	144	[120.0167; 228]
Day 14	312	[228.0167; 480]

Statistical Analysis Plan

CLI-10067AA1-01

Final Analysis

Final 1.0 of 30MAY2024

Day 28	648	[480.0167;984]
Day 56	1320	[984.0167;1656]
Day 84	1992	[1656.0167;∞)

Vital signs and oxygen saturation:

Before and during infusion:

Analysis time point window	Target time vs. start of infusion (minutes)	Time interval (minutes)
Pre-dose	<0	Last day 1, pre-dose assessment
0.25h	15	[1;22]
0.5h	30	[23;37]
0.75h	45	[38;52]
1h	60	[53;67]
1.25h	75	[68;82]
1.5h	90	[83;97]
1.75h	105	[98;112]
2h	120	[113;127]
2.25h	135	[128;142]
2.5h	150	[143;157]
2.75h	165	[158;172]
3h	180	[173;187]
3.25h	195	[188;202]
3.5h	210	[203;217]
3.75h	225	[218;232]
4h	240	[233;247]
4.25h	255	[248;262]
4.5h	270	[263;277]
4.75h	285	[278;292]

Statistical Analysis Plan

CLI-10067AA1-01

Final Analysis

Final 1.0 of 30MAY2024

5h	300	[293; 307]
5.25h	315	[308; 322]
5.5h	330	[323; end of infusion]

After infusion:

Analysis time point window	Target time vs. end of infusion (minutes)	Time interval (minutes)
0h	0	[End of infusion; 5]
0.5h	30	[6;45]
1h	60	[46;90]
2h	120	[91;150]
3h	180	[151;210]
4h	240	[211;300]
6h	360	[301;420]
8h	480	[421;840]
20h	1200	[841;1560)

Systemic markers:

Analysis time point window	Target time vs. end of infusion (pre-dose) or start of hypersensitivity reaction (post-dose) (minutes)	Time interval (minutes)
Pre-dose	<0	Last day 1, pre-dose assessment
1h	60	[1;90]
2h	120	[91;∞)

Per parameter and analysis window, the value closest to the target time will be used in analysis tables and figures, other values will only be listed. If more than one value is located at the same distance from the target, then the latest in time will be selected. The value latest in time will be identified using, in order of preference, the assessment time, the visit and time point label or the group identifier. Missing values are removed before the selection is made.

Partially missing assessment dates or times disabling allocation to analysis windows will not be imputed and thus these assessments will not be considered in the per-time point analysis, except for the derivation of the worst.

6.2.5 *Worst-case*

A worst-case analysis visit (presented in the analysis as ‘At Any Time Point’, or similar) will be created for parameters for which abnormalities are defined to summarise values considered as the worst-case.

The worst-case analysis visit will be derived within the treatment phase, including scheduled and unscheduled assessments as well as the early termination visit assessments. Only post-baseline assessments will be considered for the worst-case analysis visit.

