7.2.1.2 Determination of CHF10067

Blood samples (1 sample = 3.5 mL) for determination of serum CHF10067 will be collected at the following timepoints: pre-dose (within 75 minutes from start of infusion), at the end of infusion, 2, 4, 8, and 20 hours after the end of infusion and 5, 7, 14, 28, 56, and 84 days post-dose. The selected timepoints are based on the results obtained after single dose in healthy subjects. Timepoints may be adjusted during the study if the PK profile in IPF patients is significantly different than healthy subjects. In that case, decisions will be taken by the Safety Advisory Committee and appropriately documented. The total number of timepoints is not expected to be modified.

The time deviation window for PK sampling will be:

- \pm 5 minutes for timepoints \leq 2 hours
- \pm 15 minutes for timepoints $>$ 2 hours and \leq 8 hours
- \pm 1 hour for the timepoint of 20 hours
- \pm 1 day for Days 5 and 7
- \pm 2 days for Days 14, 28, 56, and 84.

The processing, storage and shipment of samples are detailed in the Laboratory Manual document.

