2.1.4 Presentation of results

Listing

The actual sampling date/time and the actual time of end of infusion will be listed per subject, dose level and analysis time point. For samples that are reallocated to another analysis time point window, the new analysis time point window will be presented in “Analysis Time Window” column. Additionally, individual PK concentrations will be presented. PK concentrations excluded from PK parameter estimation and/or descriptive statistics will be marked and clarified with a remark. Important time deviations will be reported with elapsed time from planned timepoint in “Remarks” column.

	Statistical Analysis Plan	
CLI-10067AA1-01	Final Analysis	Final 1.0 of 30MAY2024

Subjects that are excluded from the PK set and/or PK data that is excluded from PK parameter estimation, descriptive statistics and/or inferential statistics will be listed per subject, dose level and concentration time point or PK parameter, with the reason for exclusion. If this reason is due to an important protocol deviation, it will be marked too.

Tables

Individual actual sampling time points relative to end of infusion will be tabulated, per dose level. Important time deviations will be marked in the table with appropriate footnoting. Missing sampling times will be reported as “NT” (no time). Missing samples will be reported as “NS” (no sample).

Individual serum concentration data together with descriptive statistics will be tabulated, per dose level at each allocated analysis time point window. A footnote will be added to specify that a time windowing approach was considered to assign samples to the analysis time point. Missing samples or samples missing in an analysis time point window due to reallocated to another analysis time point window will be reported as “NRS” (no sample or reallocated sample). Samples for which no result is available will be reported as “NR” (no result). Exclusion of PK concentrations from descriptive statistics is described in section 6.1.3.1.

Individual PK parameters together with descriptive statistics will be tabulated, per dose level. Not estimable PK parameters will be reported as “NE” (not estimated). Exclusion of PK parameters from descriptive statistics is described in section 2.1.2 and section 6.1.3.1.

For the dose proportionality assessment on CHF10067 AUC_{0-t}, AUC_{inf}, and C_{max}, the slope and 90% CI of the power model will be tabulated.

Figures

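### The SAP's end-of-infusion PK window starts at 0 min, so a sample drawn 1 to 5 min early, which the protocol accepts, has no analysis window

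*SAP*

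**What the plan says.** Protocol 7.2.1.2 schedules serum samples before dosing and "at the end of infusion, 2, 4, 8, and 20 hours after the end of infusion", then on Days 5 to 84. Its sampling tolerance is plus or minus "5 minutes for timepoints" up to and including 2 hours, which covers the EOI sample. It also allows plus or minus "1 day for Days 5 and 7".

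SAP 6.2.4 assigns PK concentrations to analysis time points by elapsed time after the end of infusion. It states that "all assessments, including unscheduled assessments, will be allocated to analysis windows". The EOI row is "0 min; 10 min=0.1667", and the 2 h row starts at 11 min. The only row below zero is the pre-dose row, whose interval is "Last day 1, pre-dose assessment". Within a window, "the value closest to the target time will be used in analysis tables and figures, other values will only be listed".

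For the concentration table, SAP 2.1.4 says: "Missing samples or samples missing in an analysis time point window due to reallocated to another analysis time point window will be reported as" NRS. PK parameters are derived from actual sampling times (SAP 2.1.2 and 6.2.4).

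**The concern.** The protocol's tolerance runs on both sides of the end of infusion, but the SAP's window covers only the late side. A site that draws 3 minutes before the pump stops has followed the protocol, yet the SAP has no row for the result.

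The affected outputs are the EOI row of the concentration table (Table 14.2.2.2) and the mean concentration-time figures (Figures 14.2.2.1 and 14.2.4.1), which serve the secondary PK objective. SAP 6.1.3.1 expects t_max within 1 hour of the end of infusion, and EOI is the only scheduled sample in that hour, so the gap falls on the peak row.

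Two outputs could also disagree. A subject could have C_inf and C_max in the parameter table, taken from the early draw, and no EOI value in the concentration table. The code NRS would describe that cell badly, because the sample was neither missing nor moved to another window.

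**Working it through.** **Inputs**

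- EOI tolerance: -5 to +5 min (Protocol 7.2.1.2).
- EOI window: 0 to 10 min. 2 h window: 11 min to 3 h (SAP 6.2.4).
- Pre-dose row: pre-dose assessments only (SAP 6.2.4).
- Time resolution: whole minutes (SAP 2.1.2).
- Active subjects per dose: 6 (Protocol 12.1).

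**Step 1. How the plan's cut-points were set.** The rule appears to be the midpoint of adjacent targets. For Day 5 and Day 7 this gives (96 + 144)/2 = 120 h, as stated. Nine of the ten boundaries between post-dose windows equal the midpoint. The exception is EOI/2 h: the midpoint is (0 + 2)/2 = 1 h, but the stated cut is 10 min. The EOI window was therefore set by hand.

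**Step 2. Allocate each in-tolerance minute of the EOI sample.**

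| Minutes from end of infusion | Count | Window under SAP 6.2.4 |
|---|---|---|
| -5 to -1 | 5 | none |
| 0 to +5 | 6 | EOI |

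So 5 of 11 in-tolerance minutes have no window.

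**Step 3. The other samples up to 20 h and from Day 14.** The tolerances for 2 h, 4 h, 8 h, 20 h and Days 14, 28, 56 and 84 lie wholly inside their windows. For example, the 2 h sample may fall at 115 to 125 min, inside 11 to 180 min. Day 14 may fall at 312 ± 48 = 264 to 360 h, inside 228.0167 to 480 h.

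**Step 4. Effect per subject.** Each early draw takes the EOI count at that dose from 6 to 5, a loss of 1/6 = 16.7% of the planned values. Two early draws leave 4 of 6.

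**Step 5. After the change.** With an EOI window of -5 to +10 min, all 11 in-tolerance minutes fall in EOI. Nothing overlaps, because the row above takes only pre-dose samples and the row below starts at 11 min.

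**Step 6. Day 6, for completeness.** Hours after the end of infusion on Day 6 = 120 + visit clock time - end-of-infusion clock time. The clock times here are assumed, because the infusion duration is not in the available text.

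- Infusion ends at 14:00 and the Day 7 visit is held on Day 6 at 09:00: 120 + 9 - 14 = 115 h, in the Day 5 window. It is 115 - 96 = 19 h from the Day 5 target and 144 - 115 = 29 h from the Day 7 target.
- If the Day 5 sample was drawn at 09:00 on Day 5 (96 + 9 - 14 = 91 h, 5 h from target), it is kept. The 115 h sample is then only listed, and the Day 7 cell is empty.
- If no sample in that window is closer to 96 h, the 115 h value is shown under Day 5.
- If the tolerance means exactly 24 h either side of 144 h, the Day 7 sample may fall at 120 to 168 h. Only a draw at exactly 120 h goes to Day 5, which is 1 of 48 × 60 + 1 = 2,881 minutes.

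**The case against.** The best defence is that little depends on these windows. Every sample is listed with its actual time, and SAP 2.1.4 also tabulates sampling times relative to the end of infusion. AUC, C_max, CL, Vz, t½ and the power model do not use the windows. All of that stands, and it limits the point to one row of a table and the matching point on the mean figures. It does not close the gap: the SAP promises to allocate all assessments, and here it cannot.

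Three stronger readings are tempting, and the documents do not support them.

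- **That valid samples are discarded.** They are left out of a by-time-point summary and kept everywhere else.
- **That the Day 5/Day 7 cut is a second error.** The 120 h cut is the exact midpoint of the two targets. SAP 2.1.4 provides openly for reallocation, with a code, a footnote and a listing column. A loss needs a calendar-day reading of the 1-day tolerance and a competing sample closer to target. Keeping the eCRF visit label instead would put a 115 h concentration in the 144 h row, which exchanges one flaw for another.
- **That a sizeable share of EOI values will be lost.** Nothing in the documents says how often the draw precedes the recorded stop.

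**Conclusion.** The point holds for the EOI window and is minor. A sample drawn 1 to 5 minutes before the end of infusion is valid under the protocol and has no window in the SAP. It drops out of the EOI row and the mean figures but can still supply C_inf and C_max. The size is 5 of 11 in-tolerance minutes, and one sixth of the planned EOI values at a dose for each subject affected. How many subjects that will be cannot be said from the documents.

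This rests on two readings. The EOI sample is taken to come under the protocol's tolerance for time points up to 2 hours. The permitted window in SAP 6.1.3.1, outside which C_inf, C_max, t_max and the AUCs are set aside, is taken to be the protocol's sampling tolerance and not the analysis window. On that second reading the PK parameters and the dose-proportionality analysis are untouched.

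The Day 6 matter is a trade-off that the sponsor may wish to look at, not a fault in the plan.

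**What to change.** In the pharmacokinetics table of SAP 6.2.4, change the EOI interval from 0 to 10 min to **-5 to 10 min**, measured from the end of infusion. The pre-dose row and the 2 h row stay as they are. A draw earlier than -5 min is out of tolerance and remains a case for the data review.

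The cost is one table cell and the matching line of code. No PK parameter, listing or model changes.

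Optional: at the data review meeting, look at any Day 5 or Day 7 sample drawn on Day 6 and record in the data review report which row it is summarised in. No change to the window table is needed for this.

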6.3 IMPUTATION AND ROUNDING RULES

6.3.1 *Missing values*

No imputation of missing values will be done (i.e., observed cases analysis), except missing pre-dose concentrations will be imputed per rules below for PK parameter derivation only:

- The missing pre-dose PK concentration will be set to 0 for PK parameter derivation.

6.3.2 Handling partially or completely missing dates in calculations

Partially missing date of date of diagnosis or end date of the most recent exacerbation will be imputed as follows for the calculation of time since event:

- Missing day will be imputed with 1
- Missing day and month will be imputed with 1JAN

6.3.3 Values below or above a threshold

Safety values expressed as below (or above) the limit of quantification will be imputed by the value of the quantification limit itself. Listings will always show the non-imputed values.

PK concentrations below the quantification limit will be flagged as BLQ in the concentration and parameters tables. All BLQ values will be considered as 0.00 for PK and descriptive statistical analyses.

6.3.4 Rounding of derived variables

Derived variables will be rounded at display level:

- AE duration will be presented with 1 decimal.
- Mean of duplicates/triplicates will be rounded to the nearest integer.
Note: since the rounding is applied at display level, in the listings, the change from baseline could be slightly different to the listed value at time point t – baseline value
- Relative change from baseline will be presented with 1 decimal.
- Time since diagnosis, last exacerbation will be presented with 1 decimal.
- Derived laboratory differential values will be presented with 1 decimal.
- Log-transformed values will not be rounded.
- PK concentrations and parameters (as well as descriptive statistics) will be presented in tables with 3 significant digits except values >1000, which will be presented without decimals and t_{max} which will be presented with 2 decimals.

6.3.5 Outliers

Potential outliers will be discussed during the review of the data by the Chiesi team. Decisions on whether values are to be excluded from the analysis will be fully documented in the DRR and/or PK DRR.

6.4 PRESENTATION OF RESULTS

6.4.1 *Calculation of descriptive statistics and percentages*

For continuous parameters, full descriptive statistics will only be presented if there are at least 2 non-missing observations. Alternatively, only the number of non-missing data points and mean are shown.

Descriptive statistics of non-PK data will include the number of non-missing data points, the arithmetic mean, the standard deviation (SD), the median, minimum and maximum.

Descriptive statistics of safety parameters will additionally include 95% (or 90%) confidence interval (CI) on the mean (based on t-distribution, without continuity correction).

Mean, median, SD and CI will be presented with one more decimal place than the individual values, with a maximum of 4 decimal places. Minimum and maximum will be presented with the same number of decimal places as the individual values, with a maximum of 3 decimal places.

Descriptive statistics of PK concentrations will include the number of non-missing data points, the arithmetic mean, SD, the median, minimum and maximum and the coefficient of variation (CV) % of arithmetic mean. If more than half of values are BLQ at a specific timepoint, then SD and CV% will not be calculated and reported as “NC” (not calculated) in the tables.

Descriptive statistics on PK parameters will additionally include geometric mean and geometric CV%, except t_{max} for which the descriptive statistics will include the number of non-missing data points, the median, minimum and maximum.

The descriptive statistics on PK data will be presented as described in section 6.3.4.

The slopes and their 90%CI from the power model on PK parameters will be presented with two decimals.

For event-type data, the denominator will be all subjects in the analysis set and phase. All treatments will be shown, even if no events are present.

For frequency tabulations and cross-tabulations, missing values will not be included in the denominator count when computing percentages. For cross-tabulations of post-baseline results versus baseline results, a ‘missing’ category will be shown for baseline results if applicable.

Percentages will be shown with one decimal place.

6.4.2 Presentation of treatments

The following treatment labels will be used in the tables, listings and figures:

- CHF10067 1000 mg
- CHF10067 2000 mg
- CHF10067 3000 mg
- CHF10067 Total ⁺
- Placebo ^{*}
- Overall [#]

⁺ “CHF10067 Total” is the combination of “CHF10067 1000mg”, “CHF10067 2000mg” and “CHF10067 3000mg” treatment groups, will be shown for all demographics and safety tables (with the exception of disposition, analysis set, protocol deviations and PK).

^{*} All placebo subjects (from all cohorts) will be pooled into one “Placebo” group for presentation in tables and figures.

[#] Unless specified otherwise, an “Overall” column, to summarise all subjects over treatments (including placebo), will be presented only in tables showing data that are not affected by the study treatment (i.e., general characteristics analyses). The overall column will be shown last.

